1. REPORTING & ANALYSIS PLAN SYNOPSIS

Overview	Key Elements of the RAP
Purpose	The purpose of this reporting and analysis plan (RAP) is to describe: 
 Planned analyses and output for the final data.
Protocol	
 This RAP is based on Protocol Amendment 1(Dated: 05/JAN/2017) of study 202062 (GlaxoSmithKline Document Number 2016N288743_01)
Primary Objective	
 To assess the safety and tolerability of single and repeat doses of GSK2292767 as a dry powder in healthy cigarette smokers.
Primary Endpoint	
 Safety and tolerability of GSK2292767 as assessed by clinical monitoring of: 
 Vital Signs Spirometry Electrocardiogram (ECG) Laboratory safety data Adverse events (AEs)
Study Design	
 This is a two part, single site, randomised, double-blind (sponsor open), placebo controlled study in healthy smokers. Part A will consist of two 3-period interlocking cohorts. Part B is planned to follow Part A and is a parallel group design. The highest well tolerated dose achieved in Part A will be selected for Part B.
Planned Analyses	
 All decisions regarding final analysis, as defined in this RAP document, will be made prior to Database Freeze (unblinding) of the study data.
Primary Analysis Population	
 Primary: Safety Population (Comprised of subjects who receive at least one dose of study treatment and will be based on the treatment which the subject actually received).
Estimation	
 An estimation and inference approach will be adopted to evaluate the objectives.
Primary Analyses	
 Safety data will be presented in tabular and/or graphical format and summarised descriptively according to GSK's Integrated Data Standards Library (IDSL) standards.

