8.1.5.1. Statistical Analysis of Dose Proportionality

The following pharmacokinetic statistical analyses will only be performed if sufficient data are available (i.e. if more than 6 subjects have well defined plasma profiles). If the dose with limited data is at the lower end of the dose range, the data will be excluded and the appropriate analysis conducted on the rest of the data. However if there are non-calculable PK parameter data at intermittent doses no statistical analyses will be performed. A minimum of 3 doses will be required to assess dose proportionality. The assessment of dose proportionality will utilise Part A data only.

Pharmacokinetic Statistical Analyses for Dose Proportionality: Power Method
Endpoint(s)

 AUC(0-t), C_τ, C_{max} Each endpoint to be assessed separately.
Model Specification

 $\log_e(Y) = \beta \times \log_e(\text{dose}) + \log_e(\alpha)$ where Y is the pharmacokinetic parameter and $\log_e(\alpha)$ is an intercept term.
Model Checking & Diagnostics

 Refer to Appendix 8: Model Checking and Diagnostics for Statistical Analyses.
Model Results Presentation

 The coefficient of the slope with 90% confidence intervals, on the log scale, will be calculated, using the pooled estimate of variance, and used to assess dose proportionality. Point estimates and confidence intervals for the slope will be reported to 2 decimal places

The ANOVA method will also be used to assess dose proportionality.

Pharmacokinetic Statistical Analyses for Dose Proportionality: ANOVA Method
Endpoint(s)

 • AUC(0-t), C_τ, C_{max} • Each endpoint to be assessed separately.
Model Specification

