
 • The PK parameter will be dose-normalised prior to log_e-transformation by multiplying by reference dose / dose • Dose will be fitted as a fixed effect, subject as a random effect using DDFM=KR. • Separate lines will be fitted for each cohort by including terms for cohort and cohort*log_e(dose). If the slopes are not significantly (p-value<0.05) different from each other, the interaction term will be removed and a single slope estimate obtained. If the slopes are significantly different from each other, a separate slope estimate and associated 90% confidence interval will be reported for each cohort. • The reference dose will be chosen based on the lowest clinically relevant dose over which PK can be adequately described, with each other dose as the test doses in the construction of the ratio $\mu(\text{test})/\mu(\text{reference})$.
Model Checking & Diagnostics

 • Refer to Appendix 8: Model Checking and Diagnostics for Statistical Analyses.
Model Results Presentation

 • Point estimates for the adjusted means on the log_e scale, the mean difference between each dose (test) and the reference dose and associated 90% confidence interval will be constructed using the residual variance. These will not be presented. • The point estimate and confidence interval will then be exponentially back-transformed to allow the presentation of the adjusted (least square) geometric means for each treatment (dose), and point estimates and associated 90% confidence intervals for the ratio test/reference. • Point estimates and 90% confidence intervals for AUC, C_{max} and C_τ will be reported to 2 decimal places Treatment ratios and 90% CIs will be plotted by dose. • Plots will also be provided showing the adjusted geometric mean ratio of test to reference treatment (dose) for AUC(0-∞), AUC(0-t), C_τ and C_{max} together with 90% confidence interval.

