10.8. Appendix 8: Model Checking and Diagnostics for Statistical Analyses

10.8.1. Statistical Analysis Assumptions

Endpoint(s)	
 • Dose proportionality, accumulation, peak to trough ratio, PIP3 Ratio
Analysis	
 • Mixed effects models

 • The Kenward and Roger method for approximating the denominator degrees of freedom and correcting for bias in the estimated variance-covariance of the fixed effects will be used. • An unstructured covariance structure for the R matrix will be used by specifying 'type=UN' on the REPEATED line. 
 ○ In the event that this model fails to converge, alternative correlation structures may be considered such as CSH or CS. ○ Akaike's Information Criteria (AIC) will be used to assist with the selection of covariance structure. • Distributional assumptions underlying the model used for analysis will be examined by obtaining a normal probability plot of the residuals and a plot of the residuals versus the fitted values (i.e. checking the normality assumption and constant variance assumption of the model respectively) to gain confidence that the model assumptions are reasonable. • If there are any departures from the distributional assumptions, alternative models will be explored using appropriate transformed data. 	

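### The dose-proportionality power model is written without a subject or cohort term, and the SAP passages that could supply them conflict; a literal fit gives a slope interval that is not a 90% interval

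*SAP*

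**What the plan says.** On design, the SAP synopsis states: "Part A will consist of two 3-period interlocking cohorts". Section 8.1.5.1 adds: "The assessment of dose proportionality will utilise Part A data only".

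The power-method box in 8.1.5.1 sets the natural log of Y equal to beta times the natural log of dose plus a log-alpha intercept, "where Y is the pharmacokinetic parameter and" log-alpha is the intercept. Nothing else is in the model line. For the result: "The coefficient of the slope with 90% confidence intervals, on the log scale, will be calculated, using the pooled estimate of variance". That slope and interval are what the box uses to judge dose proportionality. Under model checking it says: "Refer to Appendix 8: Model Checking and Diagnostics for Statistical Analyses".

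The ANOVA box for the same endpoints is more explicit: "Dose will be fitted as a fixed effect, subject as a random effect using DDFM=KR". It dose-normalises the parameter before taking logs. It also contains a bullet that fits separate lines by cohort through cohort and cohort-by-log-dose terms, drops the interaction if the slopes do not differ at the 5% level, and reports one slope or one per cohort with a 90% interval.

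Appendix 8 (10.8.1) covers "Dose proportionality, accumulation, peak to trough ratio, PIP3 Ratio" under the analysis type "Mixed effects models". It asks for Kenward-Roger and an unstructured R matrix on the REPEATED line, with CSH or CS as possible fallbacks if the model does not converge. It does not separate the power method from the ANOVA method and names no subject term.

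**The concern.** PK values from one subject at different doses are correlated. A regression with only an intercept and slope treats them as independent. It puts between-subject variance into the residual, although most of the slope information may come from within-subject contrasts.

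The omission stands out because the other model boxes (ANOVA, accumulation in 8.1.6.1, peak-to-trough in 8.1.6.2, PIP3 in 8.2.2) all name subject as random, although they too refer to Appendix 8. The authors did not generally rely on that appendix to supply the subject term.

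The slope interval of a secondary PK analysis is at stake. If it is too wide, it can hide a departure from proportionality and lose the benefit of the crossover. If it is too narrow, it can suggest a departure that is not there. Which of these arises depends on how doses are split between cohorts, and the SAP does not say.

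**Working it through.** **Is there a figure to reproduce?** No. The SAP states no slope standard error, interval width, CV, Part A cohort size or allocation of doses to cohorts. Only the display doses are given (section 10.4.1: 50, 100, 200, 500, 1000 and 2000 µg). All else below is assumed.

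**Assumptions for one worked case.** n = 12 subjects per cohort, three active doses each, CVs 50% between and 30% within subjects. Log-scale variances are s² = ln(1 + CV²):
- between: sb² = ln 1.25 = 0.2231
- within: sw² = ln 1.09 = 0.0862

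**Formulas.** Let W and B be the within-subject and between-cohort sums of squares of log dose, S = W + B, and v = sw² + 3sb² = 0.7556.
- Standard error reported by the literal fit: √[(sb² + sw²)/S], approximately
- True standard error of that slope: √[(W·sw² + B·v)/S²]
- Standard error with random subject: 1/√[W/sw² + B/v]

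**Interlocking doses (50/200/1000 and 100/500/2000).** The log doses are 3.91, 5.30, 6.91 and 4.61, 6.21, 7.60. Each subject contributes 4.497, so W = 24 × 4.497 = 107.9. The cohort means differ by 0.7675, so B = 72 × 0.3838² = 10.6, and S = 118.5.
- Reported: √(0.3093/118.5) = 0.051
- True: √[(9.30 + 8.01)/118.5²] = 0.035
- Random subject: 1/√(1252 + 14) = 0.028

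The ratio of reported to random-subject standard error is 1.8. The 90% half-width is 0.085 as written against 0.047 with random subject. Simulated coverage of the literal interval is about 98%.

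**Non-overlapping doses (50/100/200 and 500/1000/2000).** W = 24 × 0.961 = 23.1, B = 72 × 1.1513² = 95.4, S = 118.5.
- Reported: 0.050 (exact; the approximate formula gives 0.051)
- True: √[(1.99 + 72.1)/118.5²] = 0.073
- Random subject: 1/√(268 + 126) = 0.050

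The reported standard error happens to be close to the random-subject one, but the literal slope is itself less precise than that. Simulated coverage is about 74%.

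**Range.** I varied 6 to 12 subjects per cohort, CV pairs from 30/30% to 60/25% and 50/20%, and two or three active doses per subject, with 20,000 simulated data sets per case.

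| Allocation | Reported SE / random-subject SE | Coverage of nominal 90% interval |
|---|---|---|
| Interlocking | about 1.25 to 2.5 | about 93% to 99% |
| Non-overlapping | about 0.87 to 1.24 | about 71% to 84% |

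A wider interlocking grid, with CV pairs from 20/40% to 60/20%, gave ratios of 1.07 to 2.82 and coverage of 91.5% to 99.5%.

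**Do the other passages settle the model?**
- Appendix 8 points to a mixed model, but an unstructured matrix indexed by dose has covariances for pairs of doses that no subject receives in both, and these cannot be estimated. Added to a random subject intercept, it also models the same correlation twice.
- The slope text in the ANOVA box does not fit that box. On dose-normalised data, ln(Y × ref/dose) has slope beta − 1, not beta. If each dose is given in only one cohort, cohort and cohort-by-log-dose are linear combinations of the dose-level terms and cannot be estimated alongside them.

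**The case against.** The strongest reply is that no one would fit the equation literally. The power box refers to Appendix 8, which lists dose proportionality as a mixed effects analysis with Kenward-Roger and a repeated-measures covariance. The only detailed slope-fitting text sits directly below a random subject effect and looks like power-model text in the wrong box. The pooled-variance wording does not imply ordinary least squares, since section 8.2.2 uses it for the PIP3 model, which has random subject effects. The ANOVA analysis, with subject explicit, is a second assessment, and no acceptance limit is set for the slope.

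Much of this stands. A reader might infer that the SAP commits to ignoring subject and that the reported interval will therefore be wrong. The document does not support that: a fit following Appendix 8 with a workable subject covariance, such as compound symmetry, would avoid the error. Nor is twice the necessary width a typical figure; it lies towards the upper end of the assumed range.

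What does not stand is that Appendix 8 cures the gap. The power box cites it for checking and diagnostics, not for model specification. It names no subject term, and its default structure may be inestimable here.

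**Conclusion.** The point holds as an incomplete and internally inconsistent specification. The power model lacks subject and cohort terms, Appendix 8 implies a mixed model without defining one that works for these data, and the cohort slope text is in a box where it does not belong.

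The wrong interval follows only if the equation is fitted literally. Under interlocking doses, which match the synopsis description, the error is then conservative. Under non-overlapping doses the interval is too narrow for the slope it accompanies. Every size given rests on assumed CVs, cohort sizes and allocation. For a secondary PK analysis this should be corrected before unblinding; it does not touch the primary safety objective.

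**What to change.** In 8.1.5.1, write the power model with log dose, cohort and cohort-by-log-dose as fixed effects and subject as random, fitted by REML with Kenward-Roger degrees of freedom. Drop the interaction under the 5% rule now in the ANOVA box. Take the 90% interval for beta from that fit.

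In the same edit:
- move the cohort and slope bullet from the ANOVA box to the power box;
- define which variance the pooled-variance clause means, or delete it;
- state in Appendix 8 that the unstructured R matrix does not apply to the dose-proportionality models with random subject.

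The cost is a few lines of text and one RANDOM statement, with no new data. In the worked interlocking case the cohort term costs almost nothing: the slope standard error becomes √(sw²/W) = √(0.0862/107.9) = 0.028, unchanged to three decimals. With non-overlapping doses it rises from 0.050 to √(0.0862/23.1) = 0.061, because the slope then rests on within-subject information only.

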10.4. Appendix 4: Data Display Standards & Handling Conventions

10.4.1. Study Treatment & Sub-group Display Descriptors

Treatment Group Descriptions			
RandAll NG		Data Displays for Reporting	
Code	Description	Description ^[2]	Order ^[1]
A	Placebo inhaled single dose	Placebo	1
B	50ug GSK2292767 inhaled single dose	50ug OD	2
C	Dose Level 2 GSK2292767 inhaled single dose	100ug OD	3
D	Dose Level 3 GSK2292767 inhaled single dose	200ug OD	4
E	Dose Level 4 GSK2292767 inhaled single dose	500ug OD	5
F	Dose Level 5 GSK2292767 inhaled single dose	1000ug OD	6
G	Dose Level 6 GSK2292767 inhaled single dose	2000ug OD	7
H	Placebo inhaled repeat dose	Placebo	1
I	Dose Level 7 GSK2292767 inhaled repeat dose	XXXXug OD	2

NOTES:

1. Order represents treatments being presented in TFL, as appropriate.
2. Replace X's with the actual agreed dose for the cohort and period.

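### The cohort-slope test for dose proportionality sits in the categorical-dose ANOVA, where it has no degrees of freedom, and is missing from the power model that reports the slope

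*SAP*

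**What the plan says.** Section 8.1.5.1 specifies two models for AUC(0-t), Cτ and Cmax, using Part A data only.

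- **Power model.** Log parameter on log dose, with an intercept and one slope. "The coefficient of the slope with 90% confidence intervals, on the log scale, will be calculated", and this slope is what proportionality is judged on. The block contains no cohort term, no interaction and no subject effect.
- **ANOVA.** The parameter is dose-normalised and then logged. "Dose will be fitted as a fixed effect, subject as a random effect using DDFM=KR". The output is a geometric mean for each dose, plus "the mean difference between each dose (test) and the reference dose" back-transformed to a ratio.
- **Cohort rule, inside the ANOVA specification.** "Separate lines will be fitted for each cohort by including terms for cohort and cohort*log_e(dose"). If the slopes do not differ at p<0.05, the interaction is dropped and a single slope obtained. Otherwise each cohort's slope is reported with a 90% CI. The results-presentation part of the ANOVA block mentions no slope.

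Other relevant places:

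- The synopsis gives the layout: "Part A will consist of two 3-period interlocking cohorts".
- Section 10.4.1 lists active single-dose levels up to "Dose Level 6 GSK2292767 inhaled single dose", with display labels 50, 100, 200, 500, 1000 and 2000 µg.
- Section 8.1.5.1 lets doses with limited data at the low end be excluded, and adds: "A minimum of 3 doses will be required to assess dose proportionality".
- Section 10.8.1 lists "Dose proportionality, accumulation, peak to trough ratio, PIP3 Ratio" under mixed effects models with Kenward-Roger. It adds no cohort term.

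**The concern.** One adjusted mean per dose and one ratio per test dose mean that dose is a factor in the ANOVA. A factor with one parameter per dose already absorbs any line in log dose. If each dose belongs to one cohort, it absorbs separate lines per cohort as well. The slope-equality test then has nothing left to estimate, and neither the single slope nor the per-cohort slopes can be obtained from that model.

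The power model is where a slope is estimated and used, and it pools the two cohorts without any check that their slopes agree. A planned decision step is therefore attached to the model that cannot run it and absent from the model that needs it. The fault would appear at the first fit, so the repair would be chosen with the data in hand.

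**Working it through.** The plan gives no numerical figure on this point, so there is none to reproduce. The check is the rank of the fixed-effects design matrix: df of an added term = rank with the term minus rank without it.

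**Inputs.** Doses 50, 100, 200, 500, 1000 and 2000 µg (section 10.4.1). Two cohorts of three periods (synopsis), giving 2 × 3 = 6 cohort-period slots for six levels. The minimum of three doses and the exclusion of low doses come from section 8.1.5.1. Assumption: each dose is given in one cohort.

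**Algebra.** Let I(d) be the indicator of dose d.

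- cohort 2 = Σ I(d) over the doses given in cohort 2
- cohort 2 × log(dose) = Σ log(d)·I(d) over the same doses
- log(dose) = Σ log(d)·I(d) over all doses

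All three lie in the span of the dose indicators. The last identity does not depend on the allocation, so a common slope is never estimable beside categorical dose.

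**Ranks over all 20 ways of splitting six doses three and three.** ANOVA columns: dose / + cohort / + cohort×log dose. Power-model columns: intercept and log dose / + cohort / + interaction.

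| Doses kept | ANOVA | Power model | Interaction df, ANOVA | Interaction df, power model |
|---|---|---|---|---|
| All six | 6/6/6 | 2/3/4 | 0 | 1 |
| Lowest one dropped | 5/5/5 | 2/3/4 | 0 | 1 |
| Lowest two dropped | 4/4/4 | 2/3/4 or 2/3/3 | 0 | 1 or 0 |
| Lowest three dropped | 3/3/3 | 2/3/3 or 2/2/2 | 0 | 0 |

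With four doses, alternating allocation gives 2/3/4 in the power model, and sequential allocation (lowest three doses in one cohort) gives 2/3/3. With three doses at least one cohort has fewer than two, so no slope comparison exists in either model.

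**If doses were shared between cohorts.** All six levels plus one shared dose (seven cohort-dose cells): ANOVA 6/7/7, interaction still 0 df. Two shared doses (eight cells): 6/7/8, interaction 1 df. Neither fits six slots. If the six slots held fewer than six distinct levels, one shared dose would leave the interaction at 0 df, and two or three would give it 1 df. The common slope stays at 0 df in every case.

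**Numerical illustration.** One simulated data set, with assumed values: 7 subjects per cohort, true slopes 1.0 and 0.6, between-subject SD 0.4, within-subject SD 0.25, random subject effect. Adding the cohort lines to the ANOVA gives a likelihood-ratio chi-square of 0.0. Adding cohort×log dose to the power model with cohort gives 38.2 on 1 df. The ANOVA cannot see a slope difference that the power model detects at once.

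**Dose-normalisation.** log(Y × ref/dose) = log Y + log(ref) − log(dose). A slope on normalised data is therefore β − 1, with proportionality at 0 instead of 1. The slope difference between cohorts is unchanged, so this is a labelling point only.

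**The case against.** The strongest case against has four parts.

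- **The 0 df result is conditional.** It needs each dose to be confined to one cohort, and the SAP does not tabulate this. Part A doses are chosen after data review (section 3.1), and the 2000 µg group is reached only if escalation gets there, so a repeated level is not excluded. This limit stands. However, the interaction gains a degree of freedom only if at least two doses are shared, which six levels in six slots do not allow. Even then the promised single slope remains inestimable.
- **Coding and test type are not stated.** With continuous log dose, or with the cohort lines entered before dose in a sequential test, the interaction would have degrees of freedom. True, but the block states neither, and per-dose means and ratios require dose as a factor.
- **The intended home is evident.** The terms, the p<0.05 rule and both outcomes are pre-specified, and the only other model in the section is the one with a slope. This is fair and limits the harm: it reads as a misplaced bullet more than a poor choice of method. As written, both blocks are still wrong.
- **The stakes are small.** This is a secondary PK estimation analysis, run only if data suffice, and no proportionality conclusion is shown to change. This also stands. The missing subject effect in the power block is largely covered by section 10.8.1.

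**Conclusion.** The concern holds. The common-versus-separate-slopes decision yields no test in the model that contains it (0 df in all 20 allocations, with all six doses or after dropping the lowest one, two or three). It is absent from the model whose slope is used, where it would have 1 df with six or five doses. The 0 df result for the interaction rests on the inference that each dose is given in one cohort and on dose being a factor. That a single slope cannot be estimated beside categorical dose needs only the second. The correction should be made because the written rule cannot be carried out, but it concerns a secondary PK analysis only.

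**What to change.** In section 8.1.5.1:

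1. Move the cohort, cohort×log dose and slope-decision bullet from the ANOVA block to the power model, fitted to the non-normalised log parameter, and state that proportionality corresponds to slope 1.
2. Name subject as a random effect with Kenward-Roger df in the power-model block, in line with section 10.8.1.
3. State that the interaction is fitted only if both cohorts retain at least two evaluable doses, and that a common slope is reported otherwise. Without this, the three-dose minimum permits cases where the test does not exist.
4. Leave the ANOVA as dose fixed and subject random, reporting dose-normalised ratios only.

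The cost is SAP wording and model code; no data collection or design change is involved. It should be done before database freeze.

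### The dose-proportionality ANOVA gives two conflicting rules for the 90% CI of a dose ratio; the residual-variance rule, taken literally, makes between-cohort intervals too narrow

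*SAP*

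**What the plan says.** The Part A design is given in the SAP synopsis: "Part A will consist of two 3-period interlocking cohorts". The treatment table in SAP 10.4.1 lists six active single-dose levels, from 50 to 2000 µg, the last coded as "Dose Level 6 GSK2292767 inhaled single dose". Its note reads "Replace X's with the actual agreed dose for the cohort and period", which implies one agreed dose per cohort per period.

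The ANOVA method in SAP 8.1.5.1 has this model: "Dose will be fitted as a fixed effect, subject as a random effect using DDFM=KR". SAP 10.8.1 names dose proportionality among the mixed-model analyses and says that the Kenward-Roger method, "correcting for bias in the estimated variance-covariance of the fixed effects will be used". The reference is left open: "The reference dose will be chosen based on the lowest clinically relevant dose over which PK can be adequately described".

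The results part of the same block then says that "the mean difference between each dose (test) and the reference dose and associated 90% confidence interval will be constructed using the residual variance". The next bullet back-transforms that result into the reported "point estimates and associated 90% confidence intervals for the ratio test/reference". The same model block also lists a cohort term and a cohort-by-log-dose term, with only the interaction dropped if the slopes do not differ significantly.

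**The concern.** A ratio between two doses given to the same subjects is a within-subject contrast, and residual variance is the right basis for its interval when every subject has both doses. A ratio between doses given in different cohorts is a between-subject contrast, and its variance also contains the subject component. A rule that uses residual variance for every ratio is therefore wrong for the second kind.

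Elsewhere the SAP uses the term in its within-subject sense: SAP 10.4.3 derives the within-subject CV from the mean square error of the mixed model and the between-subject CV separately. So the literal reading of the results sentence is a natural one.

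At stake are the tabulated and plotted ANOVA ratios (Table 3.106 and Figure 3.104). If cohorts alternate up the dose range and the literal rule is used, a chance difference between cohorts would appear as apparently precise non-proportionality at every other dose.

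**Working it through.** The SAP states no standard error, CV or sample size for this analysis, so there is no figure of its own to reproduce.

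**How many ratios are between cohorts.** Two cohorts of three periods give six cohort-period slots. With six levels and one dose per slot, each dose is given in one cohort only, three doses to each. The reference shares its cohort with two other doses, so 3 of the 5 ratios are between cohorts, whatever the reference and the allocation. If low doses are dropped and doses alternate between cohorts (an assumption), the count is 2 of 4 with a 100 µg reference, 2 of 3 with 200 µg and 1 of 2 with 500 µg.

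**The two standard errors.** Let σ²_b and σ²_w be the between- and within-subject log-scale variances, each ln(1 + CV²).

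- Residual only: SE_r = √[σ²_w(1/n_test + 1/n_ref)].
- Mixed model: SE_m = √[c′(X′V⁻¹X)⁻¹c], with V = σ²_b ZZ′ + σ²_w I, dose as a class variable and no cohort term.
- With complete data, SE_m/SE_r for a between-cohort ratio is √(1 + σ²_b/σ²_w).
- Coverage of a nominal 90% residual-only interval: 2Φ(1.645 × SE_r/SE_m) − 1.

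**Assumptions not in the SAP.** 9 subjects per cohort; doses alternate; either every subject takes all three doses (n = 9 per dose) or placebo replaces one dose for each subject (n = 6 per dose).

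**Worked example, complete data, CV 50/20%.** σ²_b = ln 1.25 = 0.223 and σ²_w = ln 1.04 = 0.039. SE_r = √(2 × 0.0392/9) = 0.093. SE_m = √(2 × 0.2624/9) = 0.241. The ratio is 2.59, and coverage is 2Φ(0.636) − 1 = 0.475.

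**Between-cohort ratios over the range:**

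| CV between/within | SE_m/SE_r, n = 9 | Coverage | SE_m/SE_r, n = 6 | Coverage |
|---|---|---|---|---|
| 30/40% | 1.26 | 0.81 | 1.22 | 0.82 |
| 30/30% | 1.41 | 0.76 | 1.34 | 0.78 |
| 40/25% | 1.86 | 0.62 | 1.68 | 0.67 |
| 50/25% | 2.16 | 0.55 | 1.91 | 0.61 |
| 50/20% | 2.59 | 0.48 | 2.23 | 0.54 |

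At 40/25% with n = 6, SE_r = 0.142 and SE_m = 0.238. The limits are the ratio multiplied or divided by exp(1.645 × 0.142) = 1.26 under the literal rule, against exp(1.645 × 0.238) = 1.48.

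**Same-cohort ratios.** SE_m/SE_r is 1.00 with complete data and 1.08 to 1.14 with placebo in one period (residual-only coverage 0.85 to 0.87).

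**The model as specified.** In 1,500 simulated trials per setting (REML, n = 6 per dose, containment-type degrees of freedom standing in for Kenward-Roger), the mixed-model interval covered about 0.90 to 0.91 for between-cohort ratios and 0.89 to 0.90 for same-cohort ratios.

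**The cohort terms.** With dose as a class variable and each dose in one cohort, the six dose columns have rank 6, and adding two cohort columns leaves the rank at 6. Under alternating allocation the 100 versus 50 µg contrast is then not estimable, while 200 versus 50 µg is. If the cohort-by-log-dose term is kept as well, the 200 versus 50 µg contrast is also lost.

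**The case against.** A reader might infer that the reported intervals will be far too narrow. The documents do not support that. The same block fits subject as random with Kenward-Roger, SAP 10.8.1 adds the covariance correction, and the results are described as least-squares means. LS-mean differences from that model already carry subject variance for between-cohort ratios, and they cover at about the nominal level. A residual-only interval worked out separately would make the Kenward-Roger instruction pointless. The results sentence is also loose: read strictly, it has point estimates being built from a variance. All of this stands, and it turns a certain error into a conflict of wording.

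It is also fair that the size rests on assumed CVs and numbers, and that the lowest coverage comes from one corner of the range. The analysis is secondary, estimates only, and runs beside a power model. SAP 3.1 bases escalation and the Part B dose on blinded safety and preliminary PK data, not on these intervals.

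What the objection does not remove is the sentence itself, which defines the interval that is back-transformed and reported. Its meaning is further blurred by SAP 10.8.1, which asks for an unstructured R matrix, under which there is no single residual variance. SAP 8.1.6.1 shows that the accumulation analysis can be specified without the phrase.

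**Conclusion.** The point holds as a contradiction between model specification and results presentation. If all six levels are given, three of the five ratios are between cohorts; this follows from the design as stated. For those ratios the literal rule omits between-subject variance and gives intervals that are too narrow whenever subjects differ.

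How much too narrow cannot be known from the SAP. With 9 subjects per cohort, alternating doses and CVs from 30/40% to 50/20%, the true SE is about 1.2 to 2.6 times the residual-only SE, and nominal 90% coverage falls to about 82% down to 48% (normal critical value). If the programmer uses the specified model's own LS-mean differences without the cohort terms, there is no loss. With the cohort terms kept beside a class dose effect, the between-cohort ratios cannot be estimated at all, so correcting the variance phrase alone is not enough.

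**What to change.** In the ANOVA results part of SAP 8.1.5.1:

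1. Replace the phrase on residual variance with: *taken from the mixed-model standard error of the LS-mean difference (subject and residual variance components, Kenward-Roger degrees of freedom)*.
2. Confine the cohort and cohort-by-log-dose terms to the power model, where a slope is estimated, and state that the ANOVA has class dose and random subject only.
3. Footnote the ANOVA table and figure to show which ratios are within and which are between cohorts.

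The cost is a phrase, a moved bullet and a footnote, settled before database freeze. Between-cohort intervals become wider than under the literal rule. Without a cohort term, those ratios also remain open to any systematic difference between the cohorts, which the footnote lets the reader weigh.
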